5.2 PARTICIPANT DISPOSITION

Disposition summaries will be based on the ITT population.

The number of patients who enroll, discontinue, or complete the study will be summarized by treatment group and pooled placebo group. Summaries may also be produced for each individual placebo group. Reasons for premature study withdrawal will be listed and summarized by treatment group. Major protocol deviations (PDs) will be listed and evaluated for their potential effects on the interpretation of study results.

Patients will not be excluded from the analysis populations based on major PDs unless they do not otherwise meet the definitions for each population. Sensitivity analyses evaluating the impact of major PDs may be conducted if a large number of major PD's are observed during the study.

5.3 PRIMARY ENDPOINT ANALYSIS

5.3.1 Definition of Primary Virology Endpoint

The primary objective of this study is to evaluate the antiviral activity of AT-527 compared with placebo on the basis of the change from baseline in amount of SARS-CoV-2 virus RNA as measured by RT-PCR and based on the log-10 scale at specified timepoints.

The primary analysis will use the nasopharyngeal swab data. For all Cohorts, the primary analysis will be compared at Days 3, 5, and 7 and will be performed as part of the Day 10 Review (Section 5.7.1).

All cohorts will use a pooled placebo group including all patients up to the cohort being analyzed. At the end of the study, sensitivity analysis will be performed for each cohort with a combined placebo group from all cohorts (Section 5.3.3).

The primary analysis for each cohort will be tested at a one-sided 10% alpha (equivalent to a two-sided 20% alpha).

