6. STATISTICAL CONSIDERATIONS AND ANALYSIS PLAN

All primary and secondary virology and efficacy outcomes will be analyzed in the modified intent-to-treat infected (mITTi) population. The mITTi population is defined as all patients randomized in the study who received any amount of study drug and had at least one positive SARS-CoV-2 RT-PCR test result *above or equal to the limit of quantification (LOQ)* during the study, with patients grouped according to the treatment assignment at randomization.

Safety analyses will be performed on the safety evaluable population, which consists of all patients who receive any amount of study drug. In all safety analyses, patients will be grouped according to the treatment that the patients actually received rather than the treatment assigned at randomization.

For *Cohorts A–D*, the primary virology analysis will be performed as part of a Day 10 review (accompanied with key safety review if deemed necessary, further details will be included in the SAP) which is to be completed after all patients enrolled in the current cohort have completed assessments through Day 10. Other endpoints will be analyzed at the completion of each full cohort or at the completion of the study.

For *Cohorts A–D*, all analyses at the Day 10 review or at the completion of each cohort will compare each AT-527 dose group and a combined placebo group, including all placebo patients enrolled across cohorts up to the cohort being analyzed, while analyses performed at the completion of the study will compare each AT-527 dose group and a combined placebo group from *Cohorts A–D*.

For *Cohort E*, the primary virology analysis will be performed as part of a Day 14 review (accompanied with key safety review if deemed necessary, further details will be included in the SAP) which is to be completed after all patients in *Cohort E* have completed assessments through Day 14. Other endpoints will be analyzed at the completion of the cohort.

For *Cohort E*, all analyses will compare the AT-527 dose group and the placebo group from *Cohort E* only. Data from cohorts with the same dose may be pooled to further evaluate the primary endpoint as part of a sensitivity analysis. Full details of all planned tables, listings, graphs, and statistical methods will be provided in a Statistical Analysis Plan (SAP), which will be finalized prior to the end of the study.

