6.1 DETERMINATION OF SAMPLE SIZE

The primary objective of this study is to evaluate the antiviral activity of AT-527 compared with placebo. Approximately 60 patients will be randomized in a 1:1 ratio in Cohort A to receive AT-527 or placebo. Cohorts B–D will enroll approximately 40 patients in a 3:1 ratio to receive AT-527 or placebo, respectively. *Cohort E will enroll approximately 224 patients in a 1:1 ratio to receive AT-527 or placebo.*

The sample size for Cohort A–D is based on the primary endpoint of change from baseline in SARS-CoV-2 virus RNA measured by RT-PCR at a single timepoint. A sample size of 27 patients per arm (active or placebo) in the mITTi population will result in at least 80% power to detect a mean reduction in change from baseline of between 0.7 and 1.1 log₁₀ copies using a two-sample t-test for comparison of means, assuming a standard deviation of between 1.2 and 1.85 (Regeneron 2020) and based on a 1-sided 10% alpha. The sample size has been adjusted to 30 patients per arm to account for an estimated 90% SARS-CoV-2 positive rate and is based on a single-cohort comparison of AT-527 versus placebo.

For Cohort E, a sample size of 100 patients per arm (active or placebo) in the mITTi population will result in at least 80% power to detect a mean reduction in change from baseline of 0.5 log₁₀ copies using a two-sample t-test for comparison of means, assuming a standard deviation of 1.25 (deemed appropriate based on current data from WV43042) and based on a 1-sided 2.5% alpha. The sample size for Cohort E has been adjusted to 112 patients per arm to account for an estimated 90% SARS-CoV-2 positive rate. Based on emerging external data on direct acting antivirals in COVID-19 (Fischer et al 2021), a lower mean reduction in change from baseline of 0.5 log₁₀ copies has been utilized in Cohort E. A lower alpha level has also been selected to reduce the likelihood of a false positive result and enable a more robust evaluation of the antiviral activity of AT-527 at the selected dose regimen. This sample size also allows for a better characterization of the secondary endpoints.

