6.4.1 Primary Virology Endpoint

The primary objective of this study is to evaluate the antiviral activity of AT-527 compared with placebo on the basis of the change from baseline in amount of SARS-CoV-2 virus RNA as measured by RT-PCR and based on the log-10 scale at specified timepoints.

In Cohorts A-D, the change from baseline in the amount of SARS-CoV-2 virus RNA will be compared between each AT-527 group and a combined placebo group at Days 3, 5, and 7 using Analysis of Covariance (ANCOVA) with baseline virus RNA as a covariate. The treatment group least squares mean (LSM) changes, difference in LSM changes, 80% CI and p-value will be presented for each comparison. Additionally, descriptive summaries for the change from baseline will also be presented by treatment group.

In Cohort E, the change from baseline in the amount of SARS-CoV-2 virus RNA will be compared between the AT-527 group and a placebo group containing only patients from Cohort E (unpooled) at Days 3, 5, 7, and 14 using Analysis of Covariance (ANCOVA) with baseline virus RNA as a covariate. The treatment group least squares mean (LSM) changes, difference in LSM changes, 95% CI and p-value will be presented for each comparison. Additionally, descriptive summaries for the change from baseline will also be presented by treatment group.

If the data are not normally distributed, a non-parametric alternative method will be used (e.g., Mann-Whitney U test) to compare distributions.

Further details of the primary endpoint analysis will be included in the SAP, including details of any missing data handling rules for the primary endpoint.

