6.4.2 Secondary Virology and Efficacy Endpoints

The following virology and efficacy secondary endpoints will be compared between each AT-527 dose group and the pooled placebo group *for Cohorts A–D and an unpooled placebo group for Cohort E*:

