- Time to alleviation of COVID-19 symptoms, defined as the length of time taken from start of treatment to the point at which the following criterion is met and maintained for at least 21.5 hours: Score of 0 or 1 on Items 1–12 of the COVID-19 Symptom Diary (without consideration for presence of pre-existing symptoms)
- Time to alleviation of COVID-19 symptoms, defined as the length of time taken from start of treatment to the point at which the following criterion is met and maintained for at least 43 hours: Score of 0 or 1 on Items 1–12 of the COVID-19 Symptom Diary (without consideration for presence of pre-existing symptoms)
- Duration of fever, defined as the time to return to an afebrile state (temperature $\leq 37.5^{\circ}\text{C}$) maintained for at least 21.5 hours
- Frequency of COVID-19-related complications (death, hospitalization, radiologically confirmed pneumonia, acute respiratory failure, sepsis, coagulopathy, pericarditis, myocarditis, cardiac failure)
- *Frequency of hospitalizations and death (all cause)*
- Time to alleviation of an individual symptom, defined as the time taken from the start of treatment to the point at which the following criterion is met and maintained (for each individual symptom) for at least 21.5 hours:
 - Score of 0 or 1 for Items 1–12 of the COVID-19 Symptom Diary
 - Score of 0 for Items 13 and 14 of the COVID-19 Symptom Diary

All secondary endpoints will be analyzed descriptively and summary statistics will be presented. For time to event endpoints, a Kaplan-Meier plot and the median time to response will be presented along with CIs. For proportion, frequency and incidence endpoints, the number, proportion and difference in proportions along with CIs will be presented. For area under the curve (AUC) endpoints, summary statistics will be presented. Any exploratory statistical testing will be specified in the SAP as appropriate.

Rules for missing data will be specified in the SAP.

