Appendix 3: Schedule of Activities for Cohort E

- ^a Screening assessments may be performed up to 72 hours prior to Day 1 or on Day 1.
- ^b An unscheduled visit represents a visit that is not specified by the protocol but is determined to be necessary by the investigator or Sponsor (e.g., for evaluation of an adverse event). Assessments (including PK sample collection) should be performed as clinically indicated. For unscheduled visits occurring after Day 7, PK sample collection is not required.
- ^c Patients who discontinue study drug prematurely will continue to complete assessments as indicated until the end of the study. Patients who discontinue from study participation will have an early termination visit 7 (\pm 2) days after their final dose of study drug. Patients who discontinue from the study after Day 14 will not be required to complete an early termination visit.
- ^d Required follow-up information will be collected at Day 14 (\pm 2 days), and Day 33 (\pm 3 days). Patients in Cohort E are required to have an in-person visit for nasopharyngeal swab collection.
- ^e Informed consent must be documented before any study-specific screening procedure is performed.
- ^f For patients at participating sites who have provided written or electronic informed consent to participate in mobile nursing visits, this assessment or procedure may be performed by a trained nursing professional at the patient's home.
- ^g COVID-19 Symptom Diary includes questions regarding symptoms (Items 1–14) and the Patient Global Impression of Severity. Questionnaires will be self-administered before the patient receives any information on disease status, prior to the performance of non-PRO assessments, and prior to the administration of study treatment. On Day 1, the first diary questionnaire should be completed prior to the first dose. On Days 1–14, the questionnaire (including recording of temperature) should be administered twice a day (morning and evening) at the same time each day.
- ^h On Days 15–28, the questionnaire (including recording of temperature) should be completed once a day in the evening at the same time each day.
- ⁱ Includes oxygen saturation (pulse oximetry), respiratory rate, pulse rate, and systolic and diastolic blood pressure while the patient is in a supine or seated position, and temperature.

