1.2 STUDY DESIGN

This is a Phase II, randomized, double-blind, placebo-controlled study to evaluate the antiviral activity, safety, pharmacokinetics, and efficacy of selected dose regimens of AT-527 compared with placebo in non-hospitalized adult patients with mild or moderate COVID-19. If all potential cohorts are fully enrolled, the study will enroll up to approximately 220 patients at approximately 52 sites globally.

Patients will be screened up to 72 hours prior to randomization. Patients who do not meet the criteria for participation in this study (screen failure) cannot be re-screened. The investigator will record reasons for screen failure in the screening log.

Eligible patients will be enrolled sequentially into one of up to five possible treatment cohorts (Cohorts A–E). Sixty patients will be enrolled into Cohort A; Cohorts B–E will enroll 40 patients each. Patients who withdraw from the study or who discontinue study treatment will not be replaced. However, patients who withdraw from the study after screening, but before receiving the first dose, will be replaced. However, they may not receive the same treatment as the patient they are replacing.

In Cohort A, patients will be randomized in a 1:1 ratio to receive either AT-527 550 mg tablets (or placebo) twice a day (BID) on Days 1–5, with assessment visits on Days 3, 5,

and 7. After 30 patients (50% enrolment) in Cohort A have completed assessments through Day 10, an interim review of safety data will be conducted to determine the AT-527 dose and regimen for Cohort B.

In Cohorts B–E, patients will be randomized in a 3:1 ratio to receive either AT-527 or placebo on Days 1 – 5, with assessment visits on Days 3, 5 and 7. Dose regimen decisions for Cohorts C–E will be made by the Sponsor study team following unblinded review of safety data by an Internal Monitoring Committee (IMC) after 20 patients (approximately 15 active and 5 placebo) enrolled in the previous cohort have completed assessments through Day 10. The maximum dose to be tested in the study will not exceed AT-527 1100 mg BID for 5 days. Depending on emerging data, the Sponsor may also evaluate regimens with doses of AT-527 lower than 550 mg BID. Cohorts evaluating such lower doses may be initiated at any time following the Cohort A interim safety review and will not require IMC oversight.

[figure not shown]

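### The SAP analyses Cohort E under the superseded 220-patient design: pooled placebo, four times the protocol's per-test alpha, and no Day 14 comparison

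*SAP*

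**What the plan says.** **Protocol Version 6, Cohort E.**

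- Sections 3.1 and 6.1: about 224 patients, randomized 1:1.
- Section 6.1, sample size: "assuming a standard deviation of 1.25 (deemed appropriate based on current data from WV43042) and based on a 1-sided 2.5% alpha".
- Section 6.4.1: ANCOVA against a "placebo group containing only patients from Cohort E (unpooled) at Days 3, 5, 7, and 14", with a 95% CI.
- Section 6: "the primary virology analysis will be performed as part of a Day 14 review".
- Sections 6.4.2 and 6.5: secondary and safety comparisons use a pooled placebo group "for Cohorts A–D and an unpooled placebo group for Cohort E". Section 6 limits the combined placebo group to Cohorts A–D.
- Section 6.4.2.2: all-cause hospitalization and death is a secondary endpoint.
- Appendix 3: swab, saliva, serum and vital signs are scheduled at Day 14. Footnote d says: "Patients in Cohort E are required to have an in-person visit for nasopharyngeal swab collection".

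**SAP, Cohort E.**

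- Section 1.2: "Cohorts B–E will enroll 40 patients each", randomized 3:1, for a study total of about 220. Day 14 is a telephone call.
- Section 5.3.1: "The primary analysis for each cohort will be tested at a one-sided 10% alpha". Section 2 states the hypothesis at the same level, and Section 5.3.2 gives an 80% CI.
- Sections 5.3.1 and 5.3.2: placebo is pooled up to and including the cohort being analysed, and the comparison is at Days 3, 5 and 7.
- Sections 5.1 and 5.3.1: the primary analysis belongs to a Day 10 review for every cohort.
- Table 3 lists no Day 14 sample. Tables 4 (virology) and 5 (vital signs) end with a Day 7 window of Days 6–8.
- Sections 5.4, 5.4.2.2 and 5.6.1 use one placebo pool from all cohorts. Section 5.5 also uses a pooled placebo group throughout.
- Table 1 and Section 5.4.2.3 do not list all-cause hospitalization and death.
- Appendix 1 says that nothing departs from the protocol's planned analyses.

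**The concern.** The SAP does not merely leave Cohort E out. It names Cohorts B–E, or says all cohorts or each cohort, and prescribes rules for Cohort E that contradict Version 6. The two documents cannot both be followed. Because the protocol refers full statistical methods to the SAP, the SAP is what would be programmed.

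Section 6.1 of the protocol explains that the lower alpha was chosen to make a false-positive result less likely. The Day 14 visit was made in-person so that a swab could be taken. Under the SAP the first safeguard is lost. The Day 14 swab could still qualify a patient for the mITTi population, yet it would enter no primary comparison, and the virology time-to-event and AUC endpoints also stop at Day 7.

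Pooling goes wrong in both directions. Earlier placebo patients enter Cohort E's primary comparison. Cohort E's placebo patients enter the Cohort A–D secondary and safety comparisons and the end-of-study primary sensitivity analysis. The main A–D primary comparison is not affected in this way, since it uses placebo only up to the cohort being analysed.

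If the conflict is still open when data are seen, there are two documented alphas, comparators and time horizons to choose from. That risk is sharper here because both documents allow optional interim analyses that unblind the study team at treatment-group level.

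**Working it through.** **1. Each document is consistent with its own design.**

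- Protocol enrolment: 60 + 3×40 + 224 = 404. SAP enrolment: 60 + 4×40 = 220.
- Protocol Cohort E: a two-sample t-test with difference 0.5, SD 1.25, one-sided 2.5% and 100 per arm has power 80.4%. The smallest n giving 80% is 100 per arm. Inflation: 100/0.9 = 111.1, rounded up to 112 per arm, 224 in total. This reproduces Section 6.1.
- SAP design: 27 per arm at one-sided 10% has power 80.1% (0.7, SD 1.2) and 81.2% (1.1, SD 1.85); 27/0.9 = 30. This also reproduces.

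So the SAP holds a complete older design, not a slip in one number.

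**2. Error rate.** 0.10/0.025 = 4 per test. Neither document adjusts for multiplicity, and the visits are correlated within patients, so the ratio is per test and not family-wise.

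**3. Smallest significant difference.** This applies the SAP's rules to Cohort E as Version 6 enrols it. Critical difference = t × SD × √(1/n₁ + 1/n₂), with SD 1.25 in all cohorts and 90% of placebo patients evaluable.

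| Comparison | SE | t | Critical difference (log10) |
|---|---|---|---|
| Protocol: 100 v 100, one-sided 2.5% | 0.1768 | 1.972 | 0.349 |
| SAP alpha only: 100 v 100, one-sided 10% | 0.1768 | 1.286 | 0.227 |
| SAP alpha and pooling, Cohort A only filled: 100 v 100 + 0.9×30 = 127 | 0.1671 | 1.285 | 0.215 |
| SAP alpha and pooling, Cohorts A–D filled: 100 v 100 + 0.9×60 = 154 | 0.1605 | 1.285 | 0.206 |

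As an example, an observed 0.30 log10 difference with 100 per arm gives t = 0.30/0.1768 = 1.70, one-sided p = 0.046. It succeeds at the SAP's level and fails at the protocol's. Power for 0.5 log10 at 100 per arm is 80.4% at 2.5% and 93.8% at 10%.

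**4. Composition of the placebo pool.** Placebo in Cohorts A–D is 30 + 3×10 = 60 when all fill. Cohort E placebo under Version 6 is 112. Cohort E may start before the earlier cohorts are complete, so a range is shown.

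| Earlier cohorts filled | Earlier placebo in Cohort E's comparator | Cohort E share of the end-of-study pool |
|---|---|---|
| A only | 30/142 = 21% | 112/142 = 79% |
| A and B | 40/152 = 26% | 112/152 = 74% |
| A–D | 60/172 = 35% | 112/172 = 65% |

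With A–D filled, the pool used for A–D secondary and safety comparisons is 172/60 = 2.9 times the size the protocol intends.

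**5. Day 14 data.** Appendix 3 allows the visit at Day 14 ± 2, that is Days 12–16. The last virology window in SAP Table 4 is Days 6–8, so no Day 14 swab can map to an analysis timepoint. The time-to-event endpoints do not use these windows, but SAP Section 5.4.2.1 runs them through Day 7 and censors patients without an event at the final Day 7 timepoint.

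**6. Stale places in the protocol.** The synopsis Primary Analysis paragraph still gives combined placebo, Days 3, 5 and 7 and an 80% CI, with no Cohort E rule. Section 9.5 still says 220 patients. Appendix 3 footnote o lists swabs to Day 7 only, although its own table has one at Day 14.

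**The case against.** The SAP almost certainly predates Version 6: it is coherent throughout for 220 patients and still has the Day 14 telephone call. The visible text names no protocol version, and the protocol allows the SAP to be finalized up to the end of the study. A later SAP may therefore exist, and Appendix 1 may have been true of the protocol it was written against. This stands as an explanation, and nothing suggests that a safeguard was removed deliberately. It does not resolve the conflict, because the SAP supplied with Version 6 prescribes a different analysis and no later one is in the documents.

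The figures 0.227 and 0.206 combine Version 6 enrolment with SAP rules, a trial that neither document plans. That is true, but it is what would happen if Cohort E enrolled under the current protocol and was programmed from this SAP. If the SAP's enrolment were followed as well, about 27 active against 63 pooled placebo patients would be evaluable (all cohorts full, 90% positive). Power for 0.5 log10 would be 67% at one-sided 10%, or 41% at 2.5%.

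The study is described as hypothesis-generating, secondary comparisons are descriptive, and a reader could form a 95% CI from the reported standard error. The 2.5% level also appears only in the sample-size text. These points soften the alpha mismatch. However, the 95% CI in Section 6.4.1 corresponds to that level, and the protocol tightened Cohort E on purpose. Recalculating an interval does not restore an unpooled comparator or a Day 14 analysis, which are the more damaging differences.

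**Conclusion.** The concern holds, and the SAP is wrong as written for Cohort E. Against Version 6 it changes the sample size, allocation, comparator, alpha, interval, timepoints and review timing. It also drops one secondary endpoint, widens the Cohort A–D placebo pool, and declares no departures.

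The per-test alpha is exactly four times the protocol's. The significance threshold falls from 0.349 to 0.227 log10 from alpha alone, and to between 0.206 and 0.215 with pooling, against a target effect of 0.5. Between 21% and 35% of Cohort E's comparator would be earlier placebo patients. Between 65% and 79% of the end-of-study pool would be Cohort E patients.

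The thresholds assume 100 evaluable patients per Cohort E arm, SD 1.25 in every cohort and 90% positivity. The shares assume that Cohort E enrols to Version 6 and that between one (A) and four (A–D) earlier cohorts are full. All of it applies only if this SAP is the one used. It must be fixed before Cohort E is unblinded.

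**What to change.** **SAP, before Cohort E is unblinded.** Amend Sections 1.2, 2, 3, 5.1 (Tables 3–5), 5.3, 5.4, 5.5, 5.6 and 5.7.1 as follows.

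- Cohort E: 224 patients at 1:1, Cohort E placebo only, one-sided 2.5% alpha with 95% CI, Days 3, 5, 7 and 14, and a Day 14 review.
- Add Day 14 windows for virology and vital signs, consistent with the ±2 days in Appendix 3, and add the Day 14 samples to Table 3.
- Restrict the combined placebo group to Cohorts A–D.
- Add all-cause hospitalization and death as a secondary endpoint.
- Replace the Appendix 1 statement with one that is true of Version 6.

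If a later SAP already does this, citing it is enough.

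**Protocol.** Bring the synopsis Primary Analysis paragraph into line with Section 6.4.1, change 220 to 404 in Section 9.5, and add Day 14 to Appendix 3 footnote o.

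**Proposal, not required by the protocol.** Version 6 sets no horizon for the virology time-to-event and AUC endpoints. Extending them to Day 14 for Cohort E would make use of the added swabs.

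**Cost.** One SAP amendment and three protocol text corrections, with no extra patients and no new data. The protocol corrections follow the approval route in Section 9.7, so they may need ethics committee and regulatory submission unless they count as administrative.

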3. STUDY DESIGN

3.1 DESCRIPTION OF THE STUDY

This is a Phase II, randomized, double-blind, placebo-controlled study to evaluate the antiviral activity, safety, pharmacokinetics, and efficacy of selected dose regimens of AT-527 compared with placebo in non-hospitalized adult patients with mild or moderate COVID-19. If all potential cohorts are fully enrolled, the study will enroll up to approximately 404 patients globally.

Patients will be screened up to 72 hours prior to randomization. Patients who do not meet the criteria for participation in this study (screen failure) cannot be re-screened. The investigator will record reasons for screen failure in the screening log.

Eligible patients will be enrolled sequentially into one of up to five possible treatment cohorts (Cohorts A–E). Sixty patients will be enrolled into Cohort A; Cohorts B–D will enroll 40 patients each, *and Cohort E will enroll approximately 224 patients.*

Patients who withdraw from the study or who discontinue study treatment will not be replaced. However, patients who withdraw from the study after screening, but before receiving the first dose, will be replaced.

In Cohort A, patients will be randomized in a 1:1 ratio to receive either AT-527 550 mg (or placebo) BID on Days 1–5, with assessment visits on Days 3, 5, and 7. After 30 patients (50% enrollment) in Cohort A have completed assessments through Day 10, an interim review of safety data will be conducted to determine the AT-527 dose and regimen for Cohort B.

In Cohorts B–D, patients will be randomized in a 3:1 ratio to receive either AT-527 or placebo on Days 1–5, with assessment visits on Days 3, 5 and 7. Dose regimen decisions for Cohorts C–D will be made by the Sponsor study team following unblinded review of safety data by an Internal Monitoring Committee (IMC) after 20 patients (approximately 15 active and 5 placebo) enrolled in the previous cohort have completed assessments through Day 10. The maximum dose to be tested in the study will not exceed AT-527 1100 mg BID for 5 days. Depending on emerging data, the Sponsor may also evaluate regimens with doses of AT-527 lower than 550 mg BID. *Cohorts that evaluate regimens with AT-527 doses lower than a previously tested dose regimen will not require IMC oversight.*

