2. STATISTICAL HYPOTHESES

The primary virology analysis for this trial will evaluate the antiviral activity of AT-527 compared with placebo at Days 3, 5, and 7 to demonstrate superiority of AT-527 over placebo.

The following null and alternative hypothesis will be tested at a one-sided 0.10 significance level (equivalent to a two-sided 0.20 significance level):

$$H_0: CFB_{AT-527} \leq CFB_{Placebo} \quad \text{versus} \quad H_a: CFB_{AT-527} > CFB_{Placebo},$$

for which the CFB_{AT-527} and $CFB_{Placebo}$ refer to the decrease from baseline in amount of SARS-CoV-2 virus RNA as measured by reverse-transcription polymerase chain reaction (RT-PCR) for AT-527 and placebo at specified timepoints, respectively.

No alpha adjustments for multiple comparisons are planned.

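### The SAP tests Cohort E at one-sided 10% against pooled placebo, the protocol sizes it at 2.5% against its own placebo, and neither says which cohort decides the primary objective

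*SAP*

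**What the plan says.** There is one primary objective, antiviral activity of AT-527 against placebo, and up to five cohorts in which to assess it: "Eligible patients will be enrolled sequentially into one of up to five possible treatment cohorts (Cohorts A–E").

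**SAP.** Section 2 sets up a formal hypothesis test "to demonstrate superiority of AT-527 over placebo" at one-sided 0.10. Section 5.3.1 applies that level to all cohorts: "The primary analysis for each cohort will be tested at a one-sided 10% alpha (equivalent to a two-sided 20% alpha"). Sections 5.3.1 and 5.3.2 use, for every cohort, a placebo group pooled up to the cohort being analysed, with 80% CIs at Days 3, 5 and 7. Section 1.2 describes Cohort E as 40 patients randomised 3:1.

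**Protocol (Version 6).** For Cohorts A–D, Section 6 says the analyses "will compare each AT-527 dose group and a combined placebo group, including all placebo patients enrolled across cohorts up to the cohort being analyzed". Cohort E is different. It has about 224 patients at 1:1, sized "and based on a 1-sided 2.5% alpha" (6.1), compared with Cohort E placebo only (6 and 6.4.1), with a 95% CI at Days 3, 5, 7 and 14 (6.4.1). The reason is given in 6.1: "A lower alpha level has also been selected to reduce the likelihood of a false positive result". Section 3.1 says Cohort E uses a regimen selected from a previous cohort.

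**Both.** SAP Section 2 states: "No alpha adjustments for multiple comparisons are planned". Protocol 6.4 says the same. Neither document names a deciding cohort or says how discordant cohorts are to be read.

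**The concern.** There are two linked problems.

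First, the documents give different rules for the same Cohort E analysis: level, placebo group, confidence interval and visits. SAP Appendix 1 declares that there are no changes to protocol-planned analyses, so the difference is not acknowledged as deliberate.

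Second, even under the protocol's rule, a regimen that goes into Cohort E has already had a primary test at one-sided 10%. If the earlier test is positive and Cohort E is negative, the plan does not say which one answers the primary objective. The stricter level was chosen to make a false positive less likely. That protection is weakened if the earlier, more lenient result has equal standing.

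Shared placebo adds a question of interpretation. A placebo group that happens to do badly favours every regimen compared with it, so two positive results among Cohorts A–D are not independent confirmation.

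**Working it through.** **1. The plan's own sample sizes** (Protocol 6.1), with n per arm = 2(z₁₋α + z₀.₈)²(SD/δ)².
- Cohorts A–D, α = 0.10, δ = 0.7, SD = 1.2: 2 × (1.2816 + 0.8416)² × (1.2/0.7)² = 26.5, so 27.
- Cohorts A–D, δ = 1.1, SD = 1.85: 25.5, so 26. The stated 27 covers both cases (t-test power 80.1% and 81.2%).
- Cohort E, α = 0.025, δ = 0.5, SD = 1.25: 2 × (1.9600 + 0.8416)² × 2.5² = 98.1, so 99. The stated 100 gives t-test power of 80.4%.
- Allowing for 90% positive: 27/0.9 = 30, and 100/0.9 = 111.1, so 112.

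All reproduce. Each stated alpha is the level to which its cohort was sized.

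**2. The two Cohort E rules side by side**

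| | SAP | Protocol |
|---|---|---|
| One-sided level | 10% (5.3.1) | 2.5% (6.1, sizing) |
| Placebo | pooled across cohorts (5.3.1, 5.3.2) | Cohort E only (6, 6.4.1) |
| CI | 80% (5.3.2) | 95% (6.4.1) |
| Visits | Days 3, 5, 7 | Days 3, 5, 7, 14 |
| Size | 40, 3:1 (1.2) | 224, 1:1 (6.1) |

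**3. Two tests of one inactive regimen.** Take one earlier-cohort test at 10% and Cohort E at 2.5% with its own placebo, which makes the two independent.
- At least one positive: 1 − 0.90 × 0.975 = 12.25%.
- Earlier cohort positive, Cohort E negative: 0.10 × 0.975 = 9.75%.
- So 9.75/12.25, about 80% of the occasions with any positive result, are the case that the plan leaves unresolved.

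**4. At least one positive cohort under no effect.** Assumptions: one visit per cohort; no drift in placebo response over time; 27 evaluable active patients per cohort; cumulative evaluable placebo of 27, 36, 45 and 54 (90% of 30, 40, 50 and 60). Shared placebo correlates the tests. For Cohorts A and B:

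corr = (1/36) / √[(1/27 + 1/27)(1/27 + 1/36)] = 0.40.

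Multivariate-normal probabilities with correlations built this way:

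| Cohorts tested | P(at least one positive) |
|---|---|
| A and E (protocol) | 12.25% |
| Two dose-finding | 17.3% |
| Three dose-finding | 23.5% |
| A–D | 28.9% |
| A–E (protocol) | 1 − (1 − 0.289) × 0.975 = 30.7% |
| A–E (SAP as written, five at 10%, 63 evaluable placebo by Cohort E) | 33.7% |

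Independent tests would give 1 − 0.9⁴ = 34.4% for A–D, so the shared placebo lowers the total.

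**5. Shared placebo and apparent replication.** P(A and B both positive) = 0.10 + 0.10 − 0.173 = 0.027. Given a false positive in A, B is falsely positive with probability 0.027/0.10, about 27% instead of 10%.

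**6. Cohort E's own error.** At one visit it is 2.5% under the protocol's rule and 10% if the SAP's level is applied. With four unadjusted visits at 2.5% each, it is 4.7% to 8.7% for between-visit correlations of 0.9 to 0.3. The documents give no such correlation, so that range is assumed.

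**The case against.** The strongest reply is that this is an early-phase dose-finding study that is open about its choices. Both documents state that multiplicity is not adjusted for. The optional-interim sections call the study hypothesis-generating, Protocol 1.3 speaks of early proof of concept, and Protocol 6.1 says the A–D size rests on a single-cohort comparison. Testing each dose cohort at its own level is defensible on those terms. **This stands:** the lack of adjustment across Cohorts A–D is not the fault.

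A second reply is that the protocol already sets Cohort E apart through its own placebo, stricter sizing alpha and wider interval. Protocol 6 also treats pooling of same-dose cohorts as an optional sensitivity analysis, which places pooling below the Cohort E comparison. **This partly stands.** It shows intent, but an optional sensitivity analysis is not a decision rule, and the SAP says something different.

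A third reply is timing. The SAP describes the smaller Cohort E, and Protocol 6 allows it to be finalised up to the end of the study. That may explain the mismatch, but the SAP as it stands still gives the wrong Cohort E rule.

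A reader might go further and infer that the sponsor would claim success on any single positive cohort. No passage says so. The documents are silent, and the point rests on that silence.

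**Conclusion.** The point holds as a conflict between documents plus a missing decision rule. For Cohort E the SAP's level is four times the one to which the protocol sized it, and the placebo group differs. Neither document says whether Cohort E or the earlier test of the same regimen decides the primary objective.

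The chance of at least one falsely positive cohort runs from about 12% to 31% under the protocol, depending on how many cohorts run, and is 34% for the SAP as written. These figures assume no effect, one visit per cohort, planned evaluable numbers and no time drift.

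Three stronger readings are not supported.
- That about 30% is the expected error: it needs all of Cohorts A–D to run, and Protocol 3.1 says up to five possible cohorts.
- That Cohort E's 2.5% is inflated twelvefold (31% against 2.5%): under the protocol's rule Cohort E uses only its own patients, so its error does not depend on A–D.
- That the sample sizes are wrong: they reproduce.

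**What to change.** 1. In SAP Sections 2, 5.3.1 and 5.3.2, replace the all-cohort rule for Cohort E with the protocol's: one-sided 2.5%, Cohort E placebo only, 95% CI, and Days 3, 5, 7 and 14. Bring the SAP's Cohort E size and allocation into line.
2. In Protocol 6.4 and the SAP, state that when Cohort E is run, its comparison at one pre-named visit decides the primary objective and the other visits are supportive. Without a named visit, the 2.5% level is not held. Fix this before Cohort E is unblinded.
3. State that a positive result in Cohorts A–D does not override a negative Cohort E.
4. Keep the A–D tests at one-sided 10% with 80% CIs, labelled as nominal dose-finding results. Note that agreement between those cohorts is not independent replication, because placebo is shared.

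**Cost.** Wording only: no extra patients or samples, and no loss of Cohort E power at the named visit relative to the single-timepoint sizing. The SAP needs revising for Cohort E in any case. The price is that a positive A–D cohort alone could no longer be reported as meeting the primary objective. If Cohort E is not opened, the A–D results stand as hypothesis-generating and no comparison decides the objective.
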